#### Morphology

Involvement of the tendon is common in patients with Osgood-Schlatter, and associated signs of bursitis and severity have shown to be prognostic of a worse outcome. A series of Osgood-Schlatter patients has been described for whom less hyperemia on color doppler ultrasound was associated with milder symptoms. Hyperemia on color doppler ultrasound (ad modum modified Öhberg 1-4) will therefore be assessed for the patella tendon and tibial tubercle (yes/no) at baseline, month 3, month 5, and month 8. High inter-rater reliability of color doppler evaluations in the patella tendon has been established,, and we

are currently investigating the reliability and clinical relevance of the full ultrasound protocol being employed in the study.

#### Knee pain during loading

The pain evoked from loading the affected tissue will be measured in four different ways. Firstly, by rating the pain level after performing the Anterior Knee Pain Provocation test (we have recently shown this test to be associated with KOOS-child 'Sport/play' and NPRS, and response over time for adolescents with knee pain). Secondly, by a NPRS 0-10 rating from performing the maximal isometric knee extension strength test and the countermovement jump (maximum pain during any of three trials). Thirdly, by manual palpation of the tibial tubercle for known pain (y/n). Finally, to evaluate local hyperalgesia, specifically at the tibial tubercle, we will use handheld algometry to detect the pressure (kPa) needed to evoke pain (going from no pain to the slightest sensation of pain) on the tibial tubercle on both knees. The intra-day and intra-tester reliability has been found to be >0.98 (ICC 3.1) for two similar sites; the center of the patella and the muscle belly of the tibialis anterior in young adults with longstanding knee pain.

#### Knee function

Knee pain is known to reduce muscle function. To evaluate the capacity of the quadriceps femoris muscle inserting at the site of pain, handheld dynamometry will be used to measure maximal isometric force generation, which will be normalized to body weight and lever-length (Nm/kg). This test has shown intertester reliability of ICC: 0.76-0.96 with a low standard error of measurement (5-11%) and good validity compared to the gold standard of isokinetic strength assessment. We have recently investigated the inter-tester reliability of this test in an Osgood-Schlatter cohort and found acceptable reliability. As a measure of power and a sports-specific skill, a countermovement jump will be performed to record jump height (cm) and power-production (watts), using high-speed video analysis via a smartphone app (My Jump 2). The test has been found feasible in adolescents, been validated against the gold standard of using a force-plate, and is highly reliable. Adolescents with Osgood-Schlatter have been reported to have tighter knee-extensor muscles, but it's unclear if this is thought to be a contributing cause or derived effect or if this is merely is a characteristic of increased musculoskeletal maturation. We will compare the change in knee flexion angle, assessed by smartphone-inclinometry during a modified Thomas Test. Different apps based on the standard smartphone level-function have been investigated with near-perfect validity with other digital methods (video-analysis, digital inclinometers) and with good to excellent inter-and intra-tester reliability and low error of measurement and detectability. However, we will utilize the built-in level app in iPhone 7 (Apple, USA) as the apps investigated in the literature are no longer available for download. We have recently investigated the inter-tester reliability of using the built-in

level app in the iPhone 7 to measure the knee flexion angle in an Osgood-Schlatter cohort and found acceptable reliability.

#### Global rating of change

To assess patient-assessed improvement or worsening, we will ask participants to rate their perceived level of change from their first visit on a 7-point Likert scale ranging from 'Much worse' to 'Much better'. GROC-scales have been found to have sufficient reproducibility and responsiveness.

#### **Usual Activities**

We will ask participants to rate their problems with an important activity using the Patient-Specific Functional Scale. They are asked to name a single important activity of their own choosing. Participants then rate their functional limitation with activity on a 0 to 10 scale, where 0 corresponds to being unable to perform activity and 10 is being able to perform activity at same level as before knee pain. At follow-up assessments, participants are asked to rate the previously nominated activity on the same scale. For other conditions, the PS-FS has shown to be valid, reliable, and responsive. In addition, the EQ-D5-Y question on problems with 'Usual Activities' will be collected.

### Pain Beliefs

To capture the level of kinesiophobia, that is, the fear of pain due to movement or exercise, a type of fearavoidance behavior, the patient-reported 17-item Tampa Scale of Kinesiophobia (TSK-17) will be used. The instrument has good reliability and validity, and has demonstrated good psychometric properties when used by adolescents.

### Self-rated Health

Recent studies have shown that self-rated adolescent health is associated with death, multimorbidity, primary care utilization, medicine use, social welfare benefits, as well as persistent musculoskeletal pain. Self-rated health will be collected through the 0-100 VAS for general health. The EQ-D5-Y questions pertaining to 'Self-care' and 'Mobility' will be omitted due to low responsivenes and the question on 'Anxiety/depression' will only be used for mediation/moderator analysis and baseline descriptives. Our application of the questions on 'Usual Activities' and 'Pain/discomfort' is described early in this section. Test-retest reliability of the EQ-D5-Y has shown a percentual agreement of 70-99%.

#### **Adverse events**

The potential occurrence of adverse events (AEs) in either treatment group will be reported as amount and

[figure not shown]
proportions, and described in prose regarding severity, timing, and duration. If sufficient data is observed to complete contingency tables, the odds ratio will also be reported. See the section "Adverse event reporting and harms" for a more detailed definition of AE. Adverse events will be collected in a systematically rather than spontaneous reporting by participants by utilizing a pre-specified instrument in REDCap for each clinical visit and the telephone consultation at month 2.

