- As a few participants performed fewer than the planned 3 attempts of maximal knee extension strength test due to knee pain, the analysis of pain during testing will now consider the most painful attempt during these trials, rather a mean measure of pain across trials.

Table 3. Pilot objectives, criter	ia, results, and change	es to trial conduct	
Prespeficied Objectives	Prespeficied Criteria	Results	Changes

Potential participants refuse to enroll due to information about the study, other than randomization	≤50% (n=7/15)	33%, n=5/15	
Dropout rate	≤20% (n=3/15)	20%, n=3/15. 1 concussion 2 stopped responding/showing up	
Participants attending inclusion appointment was included in the trial	≥50% (n=8/15	87%, n=13/15	
Potential participants accepted to be randomized	≥50% (n=8/15)	100%, n=15/15	
Incidents of in-comprehension of intervention delivery or intervention materials	≤15% (n=2/15)	0%, n=15/15	
Incidents of in-comprehension of outcomes or testing procedures	≤15% (n=2/15)	0%, n=15/15	
Incidents of faulty data collection procedures (REDCap entry, sensors, scan, clinical tests)	≤5% (n=0/15)	33%, n=5/15 3 incidents of participants not fully using sensor-app 1 scanning error 1 REDcap error	
 
As sensor-app compliance is the responsibility of participants, full compliance likely cannot be achieved. Data-loss is accepted and expected to occur at same rate during the main trial
 
Index knee was not scanned, as patient recalled wrong symptomatic leg. Index knee from hereon are noted in the appointment-text for testing-staff
 
Wrong link to REDcap survey was used. Name and timepoint is hereon piped at the top of every survey
 

Safety incidents (major or minor)	0% (n=0/15)	33%, n=5/15 4 (minor) incidents of sensor-adhesive causing skin irritation 1 (minor) flare-up short- term during strength test	
 
New procedures for preventing and handling irritated skin
 
Added instructions to not push through pain during testing
 

Capacity: how many patients can we logistically handle per day/week?	≥5 enrollments weekly	2 baseline, or 3-4 follow- up appointments per day have been feasible	
Capacity: Are rooms and equipment available when needed?	Yes, or readily manageable	Yes, no issues	
Any unforeseen challenges by intervention- or outcome personnel	No, or readily manageable	Yes, no issues	
Inclusion criteria were deemed obvious and practical by inclusion staff	Yes, or readily manageable	Yes, no issues	

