# Table 10. Overview of outcome domains and prioritized hierarchy of outcomes Outcome domain Specific outcome variables

		Primary outcome		
Sport function	1.	KOOS-child 'Sport/play' 0-100 subscale (7 items)		
		Secondary outcomes		
Patient-acceptable Symtom- state	2.	PASS question (Y/N)		
Knee-related Quality of Life	3.	KOOS-child 'Quality of Life' 0-100 subscale (5 items)		
Pain intensity and frequency (Pain flares)	4.	4-week-average episodes of pain flares (≥4 on 0-10 NPRS)	11.	KOOS-child question P1 on 'Pain' subscale (1-5 Likert scale)
	5.	Worst pain past week (0-10 NPRS)	12.	Level of pain/discomfort (EQ-D5-Y 4)
Participation in sports and physical activity	6.	4-week average hours of sports participation	13. 14. 15. 16. 17.	4-week average hours of MVPA Satisfaction with extent of sports participation Pre knee pain level of sports participation Pre knee pain level of physical activity Time to return to sport (week no.)
Osgood-Schlatter morphology (ultrasound imaging)	7.	Flaviis composite severity score	18. 19. 20.	Tendinosis signs (thickening or hyperemia) Infrapatellar bursitis signs (effusion or hyperemia Hyperemia of the tibial tubercle ad modum Öhberg
Pain during knee loading	8.	Anterior Knee Pain Provocation test (0-10 NPRS)	
 
21.
 
22.
 
23.
 
24.
 
25.
 
	Pain during knee extension test (0-10 NPRS) Pressure-pain threshold at the tibial tubercle (kPa) KOOS-child 'Pain' 0-100 subscale (8 items) Known pain during manual palpation Pain during countermovement jump (0-10 NPRS)
Objective knee function			26. 27. 28. 29.	Maximal isometric knee extension strength (Nm/kg) Countermovement jump height (cm) Countermovement power (W) Knee extensor flexibility change (°)
Global rating of change	9.	7-point Likert scale	30.	Satisfaction with treatment (Y/N)
Usual activities	10.	Patient-specific function scale (NRS 0-10)	31.	Problems with usual activities (EQ-D5-Y 3)
Pain beliefs			32.	Kinesiophobia (Tampa Scale of Kinesiophobia, 17 items)
Health			33.	Self-rated health (EQ-D5-Y 0-100 VAS)
		Safety outcomes		
	1.	Any adverse events		

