### Adverse event reporting and harms {22}

In our published pilot-study and during pilot-testing the intervention in the clinic, we have not observed any adverse events suspected to be linked to undergoing the treatment, although this was not assessed systematically. Participants will be informed in writing and verbally about the blinding aspects and potential risks and discomforts of participating in the study prior to enrollment. As with usual activites, participants' symptoms may similarly temporarily flare up during testing. Especially the anterior knee provocation test is designed to provoke anterior knee pain symptoms, specifically. Also, the algometric pressure will inflict short-term low levels of pain when going from 0 to 1 on the numeral pain rating scale (0 being 'no pain' and 10 being 'worst pain imaginable'). The imaging used in the study is diagnostic ultrasound that uses highfrequency soundwaves, with no ionizing radiation exposure and no discomfort during the scan. Usual care sometimes consists of invasive therapies such as injections and surgery, or other painful modalities, such as shockwave or dry-needling, however, the treatments and advice in the in the current study are solely based on straps, cryotherapy, exercises, and advice and education, and no adverse events are expected. As such, the potential benefits (on the individual and public level) of the study far outweigh the potential risks.

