To assess potential or any suspected harms and adverse events (AEs), participants will be asked during all clinical visits and the telephone consultation at month 2, through open-ended questioning about any new symptoms or illnesses, accidents, reasons for care-seeking, and knee-related questions on pain, locking, swelling, discoloration, or clicking experienced during exercises or other trial-related procedures, whether it can be attributed to the treatment or not. In addition, Serious (grade 3-5) unexpected side effects or AEs will be reported to the Capital Regional Ethics Committee in Denmark within 7 days after the study director has become aware of the incident. All AEs will be assessed by the study director and the Medical Advisor (PH) for possible relations with the assessments and/or intervention to consider whether there is a reasonable possibility that the AE can be caused by either. The study director will be notified of new AEs by personnel responsible for interventions or outcome assessments (at month 0, 1, 2, or 13) and will telephone the participant as soon as possible thereafter for further investigation; or when consulting the participants in person at month 0, 5 or 8. When needed, the participant will be seen by the Medical Advisor (PH). Adverse events will be categorized and graded by two independent reviewers according to the severity on from Grade 1-5 Using the Common Terminology Criteria for Adverse Events (CTCAE) grading:

- 1. Mild: Asymptomatic or minor symptoms; clinical or diagnostic observations only; no intervention needed
- 2. Moderate: Minimal, local, or non-invasive intervention indicated
- 3. Severe: Medically significant but not immediately life-threatening; hospitalization or prolongation of hospitalization indicated; disabling
- 4. Life-threatening consequences (i.e., immediate risk of death); urgent intervention indicated
- 5. Death related to adverse event

The occurrence will be reported according to the Council for International Organizations of Medical Sciences thresholds of occurrence, however, the anticipated sample (n=130) will only allow to inferences regarding very common or common harms:

- Very common  $\geq 1/10$
- Common (frequent) <  $1/10 \text{ AND} \ge 1/100$
- Uncommon (infrequent) <  $1/100 \text{ AND} \ge 1/1000$

- Rare < 1/1000 AND ≥ 1/10000
- Very rare < 1/10000

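### The only named between-arm harms measure is an odds ratio conditional on the observed counts; an unconditional risk difference with an interval, with procedure-related events shown separately, would be a cheap improvement

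*Combined protocol and SAP*

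**What the plan says.** The Adverse events section, under Outcomes, begins "The potential occurrence of adverse events (AEs) in either treatment group will be reported as amount and" proportions, and has the events "described in prose regarding severity, timing, and duration". That part is unconditional. The comparative part is not: "If sufficient data is observed to complete contingency tables, the odds ratio will also be reported". The section does not define what counts as sufficient, and it does not list which tables are meant.

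Table 10 lists one safety outcome, "Any adverse events". The section Adverse event reporting and harms collects events "whether it can be attributed to the treatment or not". It has them graded from 1 to 5 and categorised by two independent reviewers, and has the study director and the Medical Advisor assess each one "for possible relations with the assessments and/or intervention to consider whether there is a reasonable possibility that the AE can be caused by either". No analysis by source or relatedness is described. On the two treatments, the same section says "and no adverse events are expected".

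In Table 3, the pilot results under safety incidents include "4 (minor) incidents of sensor-adhesive causing skin irritation" among 15 participants. The same row records that new procedures for preventing and handling irritated skin were then introduced.

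The general rules in Statistical methods prescribe logistic regression for non-numeric variables and 95% confidence intervals. They name no risk difference and no method for empty cells.

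**The concern.** There are two separate weaknesses, and they concern different tables.

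First, whether a comparison is reported depends on the data. On the usual reading, a two-by-two table with no events in one arm cannot yield a finite odds ratio, so the condition fails. That is the most one-sided pattern a harm can show. Falling back on logistic regression does not help, because it estimates the same odds ratio and has no finite maximum-likelihood solution when one arm has no events. Since the sponsor expects few or no events, sparse tables are the likely case.

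Second, if the comparison is made on any adverse event, and if minor sensor reactions count as adverse events, a background common to both arms is added to both numerators. That pulls the odds ratio towards 1 whatever the treatments do.

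The primary analysis is not affected. What is at stake is how informative the harms comparison will be in a trial of adolescents, where the protocol itself limits harms inference to very common and common events.

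**Working it through.** **Arm sizes.** The plan gives no assumed adverse event rate and no precision target for harms, so the only figure to reproduce is the sample size. A one-sided two-sample t-test with difference 9, SD 16, α = 0.05 and power 90% gives 54.82 per group, which matches the stated 54.8, rounded up to 55. Allowing for 15% dropout, 55/0.85 = 64.7, so 65 per arm and 130 in total, as planned.

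**Step 1: an empty cell.** Take illustrative counts of 5/65 and 0/65.
- Odds ratio: (5 × 65)/(60 × 0), which is not finite.
- Risk difference: 5/65 − 0 = 0.0769.
- Wilson limits: 0.0333 to 0.1678 for 5/65, and 0 to 0.0558 for 0/65.
- Newcombe lower limit: 0.0769 − √[(0.0769 − 0.0333)² + (0.0558 − 0)²] = 0.0769 − 0.0708 = 0.006.
- Newcombe upper limit: 0.0769 + √[(0.1678 − 0.0769)² + 0²] = 0.168.

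The risk difference is 7.7 points (0.6 to 16.8). With 55 per arm it would be 9.1 points (0.8 to 19.6). This shows that a usable estimate exists; it is not a claim of significance. Fisher's exact p for 5 versus 0 at 65 per arm is 0.058.

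**Step 2: how often a cell would be empty.** The chance of no event in the lower-risk arm is (1 − p)^n. The rates p are assumptions.

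| True rate p | n = 65 | n = 55 |
|---|---|---|
| 1% | 52% | 58% |
| 2% | 27% | 33% |
| 5% | 4% | 6% |

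**Step 3: dilution of an any-event table.** Let r be the irritation rate, equal in both arms and independent of treatment harm h (both assumed). The any-event risk is then 1 − (1 − r)(1 − h). The pilot gives 4/15 = 26.7% (exact 95% interval 7.8% to 55.1%) if each incident is a different participant. Table 3 reports five incidents in all as 5/15, which fits that reading but does not prove it. The harm rates are assumed.

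| Irritation r | OR, harm 15% v 2% | OR, harm 10% v 2% | OR, harm 5% v 2% |
|---|---|---|---|
| 0 | 8.65 | 5.44 | 2.58 |
| 5% | 3.22 | 2.29 | 1.46 |
| 7.8% | 2.59 | 1.92 | 1.33 |
| 26.7% | 1.54 | 1.32 | 1.11 |

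Example for r = 26.7% and 15% v 2%: risks 1 − 0.733 × 0.85 = 0.377 and 1 − 0.733 × 0.98 = 0.281; OR = (0.377/0.623)/(0.281/0.719) = 1.54. The risk difference shrinks less, because it equals (1 − r)(h₁ − h₀): 13.0 points with no irritation, 0.95 × 13 = 12.35 at 5%, and 0.733 × 13 = 9.5 at 26.7%.

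**Step 4: can both problems affect one table?** With irritation at 26.7% in the table, the chance of an empty arm is at most 0.733^65, about 2 × 10⁻⁹. At 5% irritation it is at most 0.95^65 = 4%. A pooled table can therefore almost always be completed but is diluted. A table without irritation avoids the dilution but may have an empty cell.

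**The case against.** The strongest reply is that nothing is hidden. Counts and proportions by arm are promised without condition, together with a description of severity, timing and duration, and the odds ratio comes in addition. A 5-versus-0 split would be in the report, and any reader could derive the difference and its interval. This stands. It rules out the reading that a one-arm harm would go unreported; what is missing is the planned comparative estimate.

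A reader might also infer that the plan pools sensor irritation with treatment harms and so masks the latter. The documents do not say so. No section states which events enter the odds ratio, the tables are mentioned in the plural, and every event is assessed for its relation to trial assessments or to the intervention. Pooling is an inference from the breadth of the safety outcome and of the collection rule. The data to separate the sources will exist, but no analysis using them is stated.

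The irritation rate is also uncertain. The pilot recorded incidents in a feasibility table, before the new skin procedures, so 27% may be too high for the main trial. The table above shows that dilution is already marked at 5%. The harm rates have no source in the documents.

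Finally, one might want treatment-related events as the main harms comparison. That has a cost: relatedness is judged by the study director and the Medical Advisor, both unblinded according to the section on unblinding, and the competing interests statement says some authors designed the experimental intervention. An outcome that ignores attribution avoids that judgement. This objection stands and shapes the fix.

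**Conclusion.** The point holds in a limited form. The plan names one between-arm harms measure, makes it conditional on the observed counts, and gives neither a risk difference nor a rule for empty cells. For a specific harm with a true rate of 1% to 5% in the lower-risk arm, the chance of an empty cell at 65 per arm is 52% to 4%. A comparison on any adverse event would instead be diluted if sensor irritation is counted: for assumed harms of 15% versus 2%, from an odds ratio of 8.6 to between 3.2 and 1.5 over irritation rates of 5% to 27%.

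These sizes rest on assumed harm rates, equal irritation in both arms, independence of irritation and harm, and one pilot incident per participant. The two effects are alternatives and should not be added together. The documents do not support the stronger conclusion that treatment harm would be concealed. This is a cheap improvement to harms reporting, with no bearing on the primary result.

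**What to change.** In the Adverse events section, replace the conditional odds ratio with an unconditional statement: for each arm, the number and proportion of participants with at least one event, and the risk difference between arms with a 95% Newcombe or Miettinen-Nurminen interval, reported whether or not a cell is empty. An odds ratio may be added where it is finite.

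Keep any adverse event as the main harms comparison. Beside it, give the same estimate for two subsets: events arising from trial procedures (sensor, testing) and all other events. Define these by the source of the event, not by a causality judgement, and fix the definitions in the SAP before the allocation is revealed for analysis. State explicitly that sensor skin irritation counts as an adverse event and which subset it belongs to.

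The cost is a few sentences of SAP wording and one extra table, from information the adverse event form and review already provide for. No change to sample size, visits or treatment is involved.
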